Title:

Efficacy and Safety of Citrate Anticoagulation in CRRT for Patients with Liver Failure/DysfuncTION, the CAUTION trial! A retrospective study on etiology of liver failure and their complications.

Background

Continuous renal replacement therapy (CRRT) is a crucial intervention for managing acute kidney injury (AKI) in critically ill patients. Citrate anticoagulation has become a preferred method in CRRT due to its effect in longer filter longevity and less bleeding compared to unfractionated heparin¹. However, its use in specific patient populations, such as those with liver failure or severe shock, necessitates careful evaluation.

Citrate acts as an anticoagulant by chelating calcium, an essential cofactor in the coagulation cascade, thus preventing clot formation within the extracorporeal circuit². The citrate-calcium complex is then metabolized mainly in the liver, where citrate is converted into bicarbonate, and calcium is released back into the bloodstream. This mechanism provides dual benefits: effective anticoagulation and metabolic alkalization.

Patients with liver failure present unique challenges for citrate anticoagulation. Impaired liver function can lead to the accumulation of citrate, resulting in high anion gap metabolic acidosis and hypocalcemia³. These risks underscore the need for vigilant monitoring and potential adjustment of citrate dosing in this population. The aim of the present study is to explore whether the etiology of liver failure, which can range from alcoholic liver disease to drug-induced liver injury or shock liver, influences the incidence and severity of citrate-related complications.

Methods

Study design

A retrospective cohort study will be conducted to compare the efficacy and safety of citrate anticoagulation in CRRT among patients with liver failure/dysfunction and severe shock.

Objectives

1. **Primary Objective:** To determine if the etiology of liver failure impacts the incidence of citrate-related complications in patients undergoing CRRT.
2. **Secondary Objectives:** To compare the efficacy of citrate anticoagulation in terms of renal recovery, filter lifespan, and patient survival between those with liver failure/dysfunction and severe shock.

Participants

- **Inclusion Criteria:**
 - Critically ill patients diagnosed with AKI requiring CRRT.

- Documented liver failure or significant liver dysfunction (e.g., elevated liver enzymes, bilirubin levels, or clinical diagnosis of liver failure) and clinical diagnosis of shock (NE of 0.25 μ g/kg/min and or association of second vasopressor).
- Age \geq 18 years.

Data Collection and Analysis

- Data will be collected retrospectively from medical records and CRRT logs.
- Statistical analysis will include descriptive statistics for baseline characteristics and outcomes.
- Comparisons will be made between patients with liver failure/dysfunction of various etiology using appropriate statistical tests (e.g., chi-square test, t-test, Kaplan-Meier analysis for filter lifespan).
- **Baseline Assessment:**
 - Collection of demographic data, medical history, and liver function tests (LFTs).
 - Baseline renal function tests and relevant clinical parameters.
- **Safety Assessment:**
 - **Primary Safety Endpoint:** Incidence of citrate-related metabolic complications (e.g., citrate accumulation).
 - **Secondary Safety Endpoints:**
 - Incidence of electrolyte imbalances (e.g., hypocalcemia).
 - Incidence of adverse events related to anticoagulation.
- **Efficacy Assessment:**
 - **Primary Efficacy Endpoint:** Filter lifespan (time until filter clotting).
 - **Secondary Efficacy Endpoints:**
 - Renal function recovery markers (e.g., free from renal replacement therapy).
 - Mortality

References

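### Shock liver is one of the etiologies to be compared, yet read literally the inclusion criterion puts every patient in shock, so the primary contrast can depend on how overlap patients are coded and on shock severity

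*Protocol*

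**What the plan says.** The Protocol makes etiology the exposure. The primary objective is "To determine if the etiology of liver failure impacts the incidence of citrate-related complications in patients undergoing CRRT". The Background gives examples of the etiologies, "which can range from alcoholic liver disease to drug-induced liver injury or shock liver".

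Under Participants, the liver condition can be met in several ways: "Documented liver failure or significant liver dysfunction (e.g., elevated liver enzymes, bilirubin levels, or clinical diagnosis of liver failure". The same bullet continues "and clinical diagnosis of shock (NE of 0.25", in μg/kg/min, and/or a second vasopressor.

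Under Data Collection and Analysis, "Comparisons will be made between patients with liver failure/dysfunction of various etiology using appropriate statistical tests", with chi-square, t-test and Kaplan-Meier (for filter lifespan) as examples.

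The secondary objective contrasts outcomes "between those with liver failure/dysfunction and severe shock", wording that treats the two as separate groups.

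**The concern.** One of the exposure categories is a liver injury attributed to shock, and on the literal reading of the inclusion criterion shock is present in everyone. A patient with alcoholic or drug-induced disease who enters in shock may have a shock-related injury as well. Raised enzymes alone can meet the liver condition, so entry does not separate existing disease from injury caused by the shock.

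A chi-square or t-test between etiologies needs each patient in exactly one group. Patients with both conditions must then be put on one side or the other, or dropped, and the choice can change the estimated difference.

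Severity is a second problem. The shock criterion, taken as a threshold, sets a minimum and not a common level. Patients whose livers were injured by shock may have been in deeper shock than the rest, and the Background itself lists severe shock as a state in which citrate needs careful evaluation. An unadjusted comparison leaves that difference inside the etiology effect.

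**Working it through.** **Reading the text.** The Protocol states no sample size, event rate, group size or overlap, so there is no figure to reproduce. The argument is textual:

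1. Objectives and Background: etiology is the primary exposure, and shock liver is named within it.
2. Participants: liver condition *and* shock, so on the literal reading all patients are in shock.
3. From 1 and 2: patients with another named etiology are all exposed to the cause of shock liver. Some may have both.
4. Data Collection and Analysis: the example group tests need one group per patient and adjust for nothing.

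**Illustration. Every input is assumed.** Take 100 patients with alcoholic or drug-induced disease, a share *f* of whom also have shock liver, and 100 patients with shock liver only. Complication risks are *pA* (underlying disease only), *pS* (shock liver only) and *pO* (both). The risk difference (RD) is shock liver minus underlying disease.

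- Overlap coded to underlying disease: RD = pS − [(1 − f)·pA + f·pO]
- Overlap coded to shock liver: RD = (100·pS + 100f·pO)/(100 + 100f) − pA
- Overlap excluded: RD = pS − pA

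Worked case with pA = 10%, pS = 20%, pO = 30%, f = 0.3:

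- To underlying disease: 0.7·10 + 0.3·30 = 16%, so RD = 20 − 16 = 4.0 points.
- To shock liver: (100·20 + 30·30)/130 = 22.3%, so RD = 22.3 − 10 = 12.3 points.

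Varying the overlap risk and the shock-liver risk at f = 0.3 (RD in percentage points):

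| pA / pS / pO | to underlying disease | to shock liver | excluded |
|---|---|---|---|
| 10 / 20 / 30% | 4.0 | 12.3 | 10.0 |
| 10 / 20 / 20% | 7.0 | 10.0 | 10.0 |
| 10 / 10 / 30% | −6.0 | +4.6 | 0.0 |
| 10 / 20 / 10% | 10.0 | 7.7 | 10.0 |

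Varying the overlap in the first row: at f = 0.1 the two codings give 8.0 and 10.9 points; at f = 0.5 they give 0.0 and 13.3. At f = 0 coding has no effect.

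**Power in the worked case.** For a two-sided 5% test, power = Φ[(|RD| − 1.96·SE0)/SE1], where SE0 uses the pooled risk and SE1 the separate risks. The pooled risk is 36/200 = 18% under either coding.

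- To underlying disease (100 vs 100): SE0 = 0.0543, SE1 = 0.0543, so Φ[(0.040 − 0.1065)/0.0543] = 11%.
- To shock liver (70 vs 130): SE0 = 0.0570, SE1 = 0.0512, so Φ[(0.123 − 0.1116)/0.0512] = 59%.

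The same patients and the same events give different contrasts, and the direction of the shift depends on the risk assumed for overlap patients.

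**The case against.** Five objections deserve weight.

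- **Universal shock is only the literal reading.** The Background and the secondary objective speak of liver failure and severe shock as separate populations. This stands: the text conflicts with itself and must be reconciled. It does not remove the problem, because if shock were a separate group, shock liver would straddle both.
- **Shock is not shock liver.** A reader might infer that the entry rule makes every patient a shock-liver case, or that overlap is certain. The document does not support this. The rule puts patients at risk of the label, and how many carry both conditions is unknown.
- **No single label is stated, and the list is illustrative.** Category definitions are commonly left to an SAP, which is not shown, so their absence alone is no finding. The point rests instead on two things the Protocol does state: a shock requirement beside a shock-defined category, and example tests that need one group per patient.
- **Outcome-aware coding is not stated.** A reader might infer that etiology will be assigned by someone who knows the outcomes. Retrospective collection makes that possible, but the Protocol lists medical history and liver tests at baseline, and diagnoses charted at the time would fit equally well.
- **A common shock criterion narrows variation in severity.** That is partly right, so shock liver cannot be called merely a marker of severity. Variation beyond the criterion can remain, and the example tests do not adjust for it.

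**Conclusion.** The point holds in a limited form. On the literal reading of the inclusion criterion, a shock-defined etiology is compared within a cohort in which everyone is in shock. The example tests would then make the primary contrast sensitive to the coding of overlap patients and open to confounding by shock severity.

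Its size cannot be derived from the Protocol. The illustrative gap of 4.0 against 12.3 points, and the change of sign in another case, rest wholly on assumed risks, group sizes and 30% overlap. They show that coding can matter, not that it will, nor in which direction. This is worth settling before outcomes are analysed, since etiology is the primary exposure. It does not undermine the study.

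**What to change.** 1. Reconcile the 'and' in the inclusion criterion with the secondary objective, so that it is clear whether shock is an entry condition for all or marks a comparison group.
2. Record two variables in place of one etiology label: underlying liver disease (alcoholic, drug-induced, other, none known) and shock liver (yes/no). Use only data charted before the first citrate exposure, and a rule fixed before outcomes are analysed.
3. Enter both in one regression model for citrate-related complications, with baseline vasopressor dose as a covariate.
4. Add a sensitivity analysis that recodes overlap patients to each side in turn, or excludes them.

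The cost is one more extraction column, the vasopressor dose if it is not already extracted, and a few sentences in the plan. No separate blinded assessor is needed. With four disease levels, one shock-liver flag and one linear dose term, the model has 3 + 1 + 1 = 5 coefficients besides the intercept. Some attribution judgement remains in the shock-liver flag, which is why the rule must be fixed in advance and the sensitivity analysis kept.

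### The secondary objective promises a comparison of citrate's efficacy on renal recovery and survival, but with no non-citrate group defined or compared, disease-group differences cannot isolate a citrate effect

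*Protocol*

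**What the plan says.** In the Protocol, Methods, Objectives, the secondary objective reads "To compare the efficacy of citrate anticoagulation in terms of renal recovery, filter lifespan, and patient survival"; the groups to be compared are patients with liver failure or dysfunction and patients with severe shock. The Study design paragraph, whose last word names shock as the second condition, uses the same language: "A retrospective cohort study will be conducted to compare the efficacy and safety of citrate anticoagulation in CRRT among patients with liver failure/dysfunction and severe". The title also announces efficacy.

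Under Data Collection and Analysis, the only contrast described is this one: "Comparisons will be made between patients with liver failure/dysfunction of various etiology using appropriate statistical tests". The example methods are "e.g., chi-square test, t-test, Kaplan-Meier analysis for filter lifespan".

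Under Efficacy Assessment, the primary efficacy endpoint is "Filter lifespan (time until filter clotting"). The secondary efficacy endpoints are "Renal function recovery markers (e.g., free from renal replacement therapy") and mortality.

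Another anticoagulant appears only in the Background, where the literature is said to credit citrate with "longer filter longevity and less bleeding compared to unfractionated heparin". It is not a study group.

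**The concern.** Efficacy of a treatment is a contrast between outcomes with it and without it. Asking whether efficacy differs between two disease groups is a question of effect modification, so it needs that contrast within each group. The protocol describes only outcomes under citrate, set side by side across diseases.

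For renal recovery and death this matters, because patients with different underlying disease can differ on both outcomes whatever anticoagulant is used. A group with a worse prognosis could be reported as one in which citrate is less effective, because the protocol files both outcomes under efficacy. The Background gives no counterweight. It describes citrate's benefits in terms of the filter, bleeding, anticoagulation and alkalization, and claims no effect on renal recovery or survival.

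**Working it through.** The protocol states no sample size, event rate, effect size or power, so there is no figure of its own to reproduce. The check is one of identifiability, followed by an illustration with assumed rates.

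**Step 1: what the objective needs and what the plan provides.** Comparing citrate's effect on mortality between groups A and B needs four risks: with and without citrate in A, and with and without citrate in B. The plan describes two of them, the risks with citrate in A and in B. Neither the Objectives nor Data Collection and Analysis defines or uses the other two.

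**Step 2: can the two described risks settle the question?** Write observed risk = no-citrate risk × RR, where RR is the relative risk of death with versus without citrate. So no-citrate risk = observed risk / RR. Assume, for illustration only, observed mortality under citrate of 70% in A and 50% in B.

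With the same RR in both groups:

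| RR in both | No-citrate risk, A | No-citrate risk, B |
|---|---|---|
| 0.8 | 0.70/0.8 = 87.5% | 0.50/0.8 = 62.5% |
| 1.0 | 70% | 50% |
| 1.2 | 0.70/1.2 = 58.3% | 0.50/1.2 = 41.7% |

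Benefit, no effect and harm fit the same data.

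With RR allowed to differ (B held at 1.0, so its no-citrate risk is 50%):

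| RR in A | No-citrate risk, A | Reading |
|---|---|---|
| 0.8 | 0.70/0.8 = 87.5% | citrate more effective in A |
| 1.0 | 70% | no difference in effect; gap is all prognosis |
| 1.2 | 0.70/1.2 = 58.3% | citrate less effective in A; gap is part prognosis |
| 1.4 | 0.70/1.4 = 50% | gap is all differential effect |

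The observed gap is 20 points in every row. The direction of the difference in efficacy, which is what the objective asks for, is not determined.

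**Step 3: would such a gap be declared?** Take RR = 1.0 in both groups, so that citrate has no effect. The power of a two-sided 5% test with n per group is

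Φ{[d − 1.96 × √(2p̄(1 − p̄)/n)] / √([p1(1 − p1) + p2(1 − p2)]/n)},

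where d is the difference between p1 and p2, and p̄ is their mean.

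| n per group | 70% vs 50% | 70% vs 60% |
|---|---|---|
| 50 | 53.3% | 18.0% |
| 100 | 82.8% | 31.6% |
| 200 | 98.5% | 55.5% |

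The test is valid as a comparison of mortality between groups. The error would be to call its result citrate efficacy.

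**Step 4: would adjustment help?** Adjusting for severity could narrow the prognostic difference between A and B. It leaves two risks where four are needed, so the treatment contrast is still missing.

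**The case against.** Several points on the other side stand.

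- **Prognosis is not shown to be the whole explanation.** A reader might infer that these comparisons simply measure the prognosis of the underlying diseases and say nothing about citrate. The document does not support that. Its Background gives a route by which citrate could act differently between groups: impaired hepatic metabolism leading to citrate accumulation, acidosis and low calcium. What can be said is that the two sources are mixed and cannot be separated.
- **The cohort is not shown to lack non-citrate patients.** A reader might infer that none exist. The inclusion criteria do not require citrate exposure, so CRRT patients treated without it could enter as the criteria are worded. What holds is that no such group is defined or compared.
- **The size is assumed.** The 70%, 60% and 50% rates are not in the protocol, and the power figures set the citrate effect to zero as an input. They show what could happen, not how large the bias would be.
- **Much of the harm is labelling.** The stated aim and the primary objective concern citrate-related complications by etiology and need no non-citrate group. The analysis text promises descriptive statistics and group comparisons, not a causal estimate for survival.

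The last point limits the reach of the problem but does not remove it. The objective and the endpoint classification are stated in the protocol itself, so this is not a detail left to a statistical analysis plan.

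**Conclusion.** The concern holds as a flaw in what the secondary objective claims. For renal recovery and survival, the plan can compare outcomes under citrate between disease groups. It cannot compare citrate's efficacy between them. This follows from the absence of a defined non-citrate contrast and does not depend on any assumed rate.

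The size cannot be estimated from the document. The 20-point illustration shows only that a sizeable gap is compatible with either direction of differential effect and with none.

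The reach is limited. The primary objective is untouched. Filter lifespan remains a direct measure of circuit performance, although between-group differences in it may also be confounded by disease. The conclusion assumes that no non-citrate comparison is intended, which is how the design sentence and the analysis section read.

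**What to change.** Reword the secondary objective along these lines: *To describe and compare filter lifespan, renal recovery and survival among patients receiving citrate CRRT, between the prespecified disease groups (liver failure/dysfunction etiologies, and liver failure/dysfunction versus severe shock once these groups are reconciled with the inclusion criterion that requires both).*

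The last clause is needed because the inclusion criterion, as worded, joins liver failure or dysfunction and shock with *and*. The two groups named in the objective are therefore not distinct. The rewording should keep that contrast visible until it is reconciled, not drop it silently.

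Move renal recovery and mortality out of Efficacy Assessment to a heading such as *Clinical outcomes (associations, not attributed to citrate)*, and do not report them as citrate efficacy. Keep filter lifespan as the circuit-performance endpoint, with a note that disease may confound between-group differences in it.

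The cost is protocol wording only. No data are lost and every planned comparison remains possible. The downside is a less ambitious claim.

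### Eligibility requires both liver dysfunction and shock, so the secondary comparison of liver patients with shock patients has no separable groups, and the primary population depends on the same conjunction

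*Protocol*

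**What the plan says.** Five parts of the protocol bear on who is studied and who is compared with whom.

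- **Participants, Inclusion Criteria.** One bullet covers both conditions. It lists ways of establishing liver failure or dysfunction and continues "or clinical diagnosis of liver failure) and clinical diagnosis of shock". Shock then gets its own vasopressor definition, which includes the phrase "and or association of second vasopressor".
- **Objectives, Secondary.** Citrate anticoagulation is to be compared on "renal recovery, filter lifespan, and patient survival between those with liver failure/dysfunction and severe shock".
- **Objectives, Primary.** The question is "if the etiology of liver failure impacts the incidence of citrate-related complications in patients undergoing CRRT". Shock is not mentioned.
- **Study design and Background.** The design sentence places the comparison "among patients with liver failure/dysfunction and severe shock". The Background, speaking of populations in which citrate needs care, gives examples joined by *or*: "such as those with liver failure or severe shock".
- **Data Collection and Analysis.** The only grouping named is etiology: "Comparisons will be made between patients with liver failure/dysfunction of various etiology using appropriate statistical tests". No rule assigns a patient to a liver group or a shock group.

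**The concern.** A comparison between two groups needs patients who belong to one and not the other. If eligibility demands both conditions, every patient belongs to both, and the secondary objective cannot be answered as stated. The analysis section does not help, because it never mentions a liver-versus-shock grouping.

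The same conjunction also decides the population for the primary objective. With *and*, patients with, for example, alcoholic or drug-induced liver failure who are not in shock are left out, and the etiology conclusions apply only to patients in shock. The primary objective does not state that limit. With *or*, those patients are included. In a retrospective study the criterion determines which records are pulled, so the question has to be settled before extraction.

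**Working it through.** The protocol states no sample size, rates or group sizes, so this is a check of set logic. Classify patients by liver failure/dysfunction (present or absent) and shock (present or absent), and see who is eligible under each way of reading the inclusion bullet.

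| Reading of the criterion | Liver and shock | Liver, no shock | Shock, no liver | Liver-versus-shock contrast |
|---|---|---|---|---|
| A. Liver condition *and* shock (plain reading) | eligible | none | none | No separable groups |
| B. Liver failure, *or* dysfunction with shock | eligible | liver failure only | none | No shock-only comparator |
| C. Liver condition *or* shock (not what the bullet says) | eligible | eligible | eligible | Possible, but patients with both fall in both groups |

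**Secondary objective.** Under A there are 0 liver-only and 0 shock-only patients by definition. B adds some liver-only patients but still supplies nobody with shock alone. C supplies all three kinds of patient but needs a rule for those with both conditions, and the protocol has none. A fourth possibility takes the objective to describe one joint population, with *between* used loosely for *among*. It then says *compare* without naming anything to compare, and still needs rewording. No reading makes the criterion and the objective work together as written.

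**Outcomes affected.** Matching the secondary objective to the efficacy endpoints:

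- filter lifespan is the primary efficacy endpoint;
- renal recovery corresponds to the renal function recovery markers (secondary efficacy);
- patient survival corresponds to mortality (secondary efficacy).

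That is 3 of 3 efficacy endpoints without a liver-versus-shock comparison under A. All 3 can still be compared by etiology, and the primary safety endpoint does not depend on the liver-versus-shock contrast.

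**Primary objective.** Under A the etiology comparison is made only in patients with both conditions. Under C it is made in all liver patients, with or without shock; shock-only patients have no liver etiology and cannot enter it. The analysis is feasible either way, but the populations differ.

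**Terminology.** The design sentence and secondary objective speak of severe shock, whereas the criterion asks for a clinical diagnosis of shock with a vasopressor definition attached. Nothing says whether these are the same thing.

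**The case against.** The strongest reply is that a single joint population was always meant. The design sentence and the criterion both use *and*, the title and stated aim concern liver failure and its etiology, and the analysis section compares etiologies only. The Background's *or* describes citrate use in general, not this cohort. On that view the misfit is one loosely chosen preposition in the secondary objective. This is a fair reading, and the documents do not rule it out. It does not remove the defect: the objective would still name no groups and would have to be rewritten.

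A related reply is that shock liver is a named etiology, so shock liver against other etiologies could be compared within a cohort where everyone has both conditions. That is feasible, but the secondary objective does not define its groups that way. Restating it as a comparison across etiologies would cover this case.

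It can also be said that an objective need not repeat every eligibility condition, and that restricting the cohort to patients in shock is a legitimate design choice. Both points stand. The effect on the primary objective follows from the same and/or question and is not a second, independent defect. The count of 3 endpoints likewise reflects one clause, and the zero counts follow directly from the literal criterion; they are not measured. The difference in shock terminology is largely editorial.

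A separate analysis plan does not answer the core point. It could define groups within the cohort, but it could not supply patients whom the eligibility criterion excludes.

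**Conclusion.** The concern holds. Under the plain reading of the criterion the liver-versus-shock comparison in the secondary objective cannot be made for any of its 3 outcomes, and the alternative readings do not make it workable as written. The primary etiology comparison survives, but whether it covers liver failure with shock only, or with and without shock, turns on one conjunction. The number of patients affected cannot be given, because the protocol states no counts.

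That the passages do not fit together rests on the text alone and is firm. Which population the sponsor intended is not known: a two-population intent is plausible but unproven. The point should be fixed before extraction; it does not make the primary analysis infeasible.

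**What to change.** Before any records are extracted, bring the inclusion criterion, design sentence, secondary objective and analysis section into line in one of two ways, according to the sponsor's intent.

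- **One joint population.** Keep *and*. Restate the secondary objective as a comparison across etiologies of liver failure. Say explicitly that the liver-versus-shock comparison is dropped and that the etiology conclusions apply only to patients in shock. The cost is protocol wording, the loss of that comparison, and narrower primary conclusions.
- **Two populations.** Change the connector to *or*. Define mutually exclusive groups (liver only, shock only, both) for the secondary objective and add that comparison to the analysis section. Run the etiology analysis only in patients with liver failure/dysfunction. The cost is protocol wording plus extraction of additional existing records.

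In either case, use one consistent term for shock in the objective, the design sentence and the criterion. How shock should be defined clinically is for the sponsor.

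### Every method the protocol names for comparing etiologies is unadjusted, although etiology is not randomised and the primary objective asks about its effect, so case mix could be read as an etiology effect.

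*Protocol*

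**What the plan says.** The Methods section describes a retrospective cohort, so etiology is observed and not assigned. The primary objective (Objectives) is "To determine if the etiology of liver failure impacts the incidence of citrate-related complications". The Background states the aim as exploring whether etiology "influences the incidence and severity of citrate-related complications", and mentions alcoholic liver disease, drug-induced liver injury and shock liver as examples.

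Under Data Collection and Analysis, etiology groups are to be compared "using appropriate statistical tests (e.g., chi-square test, t-test, Kaplan-Meier analysis for filter lifespan". The only other analysis statement is "Statistical analysis will include descriptive statistics for baseline characteristics and outcomes". The primary safety endpoint is "Incidence of citrate-related metabolic complications (e.g., citrate accumulation".

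The Baseline Assessment lists "Collection of demographic data, medical history, and liver function tests (LFTs" and "Baseline renal function tests and relevant clinical parameters". No passage links these variables to the comparison of etiologies. The protocol does not mention regression, stratification, matching, weighting, covariates or confounding.

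**The concern.** The question and the named methods do not match. *Impacts* and *influences* are effect words, and the primary objective is to determine, not merely to describe. Patients with alcoholic liver disease, drug-induced injury and shock liver can be expected to differ in age, comorbidity and baseline renal function. A chi-square test cannot separate such differences from etiology. If the named tests are followed as written, a case-mix difference could be reported as an etiology effect, or could hide one.

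There is a related ambiguity about the target. The Background says "Impaired liver function can lead to the accumulation of citrate", so the protocol recognises liver function as a driver of the outcome. It does not say whether a difference carried by worse liver function counts as an effect of etiology. Hepatic and shock severity may lie on the path from etiology to complication, and for shock liver they are partly the etiology itself. The total effect and the severity-independent effect need different adjustment sets, so the target should be chosen before the records are analysed.

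**Working it through.** **Which named method applies to the primary endpoint.** Kaplan-Meier is tied to filter lifespan. A t-test needs a continuous outcome. The primary safety endpoint is an incidence, so chi-square is the only named method that fits, and it is unadjusted.

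**Figures in the protocol.** It gives no sample size, event rate, significance level or case mix. There is nothing to reproduce, and every input below is an assumption.

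**Two groups.** Assume a binary pre-CRRT confounder with complication risk *hi* when present and *lo* when absent, and no etiology effect given the confounder. For confounder share *s*:

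- crude risk p = s·hi + (1 − s)·lo
- crude OR = [p₁/(1 − p₁)] / [p₂/(1 − p₂)]
- rejection probability = Φ((d − c)/SE₁) + Φ((−d − c)/SE₁), where d = p₁ − p₂, p̄ = (p₁ + p₂)/2, c = 1.96·√(2p̄(1 − p̄)/n), SE₁ = √([p₁(1 − p₁) + p₂(1 − p₂)]/n), and n is the number per group

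Example with hi/lo = 0.25/0.08, shares 80% and 30%, n = 200:

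- p₁ = 0.8 × 0.25 + 0.2 × 0.08 = 0.216
- p₂ = 0.3 × 0.25 + 0.7 × 0.08 = 0.131
- OR = (0.216/0.784)/(0.131/0.869) = 1.83
- d = 0.085, c = 0.0742, SE₁ = 0.0376
- rejection = Φ(0.287) = 61.3% (the other tail is negligible)

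| Risks hi/lo | Shares | Crude OR | Rejection at n = 50 / 100 / 200 per group |
|---|---|---|---|
| 25%/8% | 50/50 | 1.00 | 5.0 / 5.0 / 5.0% |
| 25%/8% | 60/40 | 1.28 | 7.4 / 9.9 / 15.0% |
| 25%/8% | 70/40 | 1.43 | 10.3 / 15.8 / 27.0% |
| 25%/8% | 80/30 | 1.83 | 20.1 / 35.4 / 61.3% |
| 20%/10% | 60/40 | 1.17 | 5.9 / 6.8 / 8.7% |
| 20%/10% | 70/40 | 1.26 | 7.0 / 9.0 / 13.1% |
| 20%/10% | 80/30 | 1.47 | 10.6 / 16.4 / 28.1% |

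For the 25%/8% rows, exact binomial enumeration of the Pearson test agrees within 1 percentage point.

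**Three groups**, matching the three etiologies mentioned, at 25%/8%, by simulation (4,000 runs per cell). The crude test is Pearson chi-square on 2 df. The adjusted test is the 2-df likelihood-ratio test of etiology in a logistic model containing the confounder.

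| Shares | Crude, n = 50 / 100 / 200 | Adjusted, n = 50 / 100 / 200 |
|---|---|---|
| Balanced | 5.2 / 4.5 / 5.5% | 5.8 / 5.0 / 5.7% |
| 40/50/60% | 6.6 / 8.3 / 11.2% | 6.0 / 5.3 / 5.4% |
| 40/55/70% | 8.0 / 12.8 / 20.7% | 5.1 / 6.0 / 5.2% |
| 30/55/80% | 14.8 / 28.2 / 50.0% | 5.5 / 5.6 / 4.7% |

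The simulation error near 5% is √(0.05 × 0.95/4,000) ≈ 0.3 percentage points. A repeat of the simulation agreed within simulation error, with adjusted rates of about 4.5% to 6.8%.

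Under confounding the crude error rate rises with sample size, because the bias stays fixed while the standard error shrinks.

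**The case against.** The strongest reply is that this is an omission in a protocol whose SAP is not at hand. Covariate lists and model forms commonly sit in a SAP, and the wording here is open: the tests are examples, qualified as appropriate. That limits the claim. It cannot be said that no adjustment will be done. What stands is that the protocol is not silent on the comparison: it names methods for an effect-type question, and none of them can address case mix.

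Second, reading the objective as causal is an interpretation. The aim speaks of exploring, and a purely associational restatement would remove part of the mismatch. That is fair, although the primary objective itself says determine.

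Third, the illustration proves little about this study. All inputs are assumed, and the adjusted test holds near 5% by construction, because the model contains the only confounder, measured without error. The protocol does not tie age, history or renal function to citrate complications. The one driver it does name, liver function, may be a mediator; if the total effect is the target, a difference carried by liver function is not bias. This is correct. It is the reason to state the target effect and to keep severity out of the first model.

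The shock entry criterion narrows the range of severity, but as a threshold it does not make the etiology groups alike.

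**Conclusion.** The concern holds. For its primary question the protocol in effect names only a crude chi-square test, in a non-randomised comparison worded as an effect. It does not say which effect is meant. The size of any bias cannot be derived from the protocol. Under the assumed single binary confounder and 50 to 200 patients per group, false rejection runs from 5% with balanced shares (no bias) to 61% with strong imbalance in two groups, and up to 50% in three. Moderate imbalance (60/40) with the weaker confounder gives 6–9%. These figures show what could happen, not what will. This should be fixed before the analysis, with medium confidence, since an unseen SAP may already specify adjustment.

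**What to change.** - State the intended effect first: the total effect of etiology, or its association independent of hepatic and shock severity.
- Make the primary analysis a prespecified logistic regression of the complication on etiology, with one joint test over all etiology categories. Use Firth penalisation if events are few.
- Adjust it for pre-CRRT variables already listed for collection: age, medical history items that do not themselves define the etiology, and baseline renal function.
- Report a second prespecified model that adds liver function tests, bilirubin and vasopressor support. Label it the severity-independent association, because these may be mediators or part of the etiology.
- Keep chi-square as the crude, descriptive result, and word the conclusion as an adjusted association.

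The cost is a few sentences of protocol text and slightly more analysis. The first model needs no new data, and vasopressor support is already part of the shock entry criterion. The one drawback is that few covariates can be supported if complications are rare, so the covariate list should be short and in priority order.
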